6.1 Study treatment(s)

In this study, the term “study treatment” used in the protocol refers to the investigational radioligand imaging compound [⁶⁸Ga]Ga-DOTA-TATE, which after radiolabeling with ⁶⁸Ga, serves as a radioactive PET diagnostic agent for localization of SSTR-positive tumors, and to the ⁶⁸Ge/⁶⁸Ga generator used to obtain ⁶⁸Ga as a ⁶⁸Ga chloride solution. Both study treatments have no therapeutic effect.

Due to short radioactive half-life of ⁶⁸Ga, [⁶⁸Ga]Ga-DOTA-TATE cannot be supplied as ready-to-use radiopharmaceutical. Therefore, [⁶⁸Ga]Ga-DOTA-TATE will be manufactured directly at clinical trial sites immediately prior to administration into participants by chelation of ⁶⁸Ga with DOTA-TATE supplied as a cold kit for the radiopharmaceutical preparation. The ⁶⁸Ga used for chelation will be eluted from the ⁶⁸Ge/⁶⁸Ga generator as ⁶⁸Ga chloride. [⁶⁸Ga]Ga-DOTA-TATE will be prepared as a sterile solution.

[⁶⁸Ga]Ga-DOTA-TATE will be administered intravenously at a dose of 2 MBq/kg (0.054 mCi/kg) of body weight up to a total maximum dose of 200 MBq (5.4 mCi) (refer to [Section 6.2](#) for details on handling, preparation and administration).

[⁶⁸Ga]Ga-DOTA-TATE used for PET imaging must be prepared only with the use of DOTA-TATE cold kit for the radiopharmaceutical preparation and the ⁶⁸Ge/⁶⁸Ga generator.

Sponsors or their designee will provide ⁶⁸Ge/⁶⁸Ga generator and DOTA-TATE cold kit for the radiopharmaceutical preparation of [⁶⁸Ga]Ga-DOTA-TATE.

Table 6-1 **Investigational and control drug**

Treatment Title	DOTA-TATE	⁶⁸ Ge/ ⁶⁸ Ga Generator
Type	drug	drug
Dose Formulation	Kit for radiopharmaceutical preparation	Radionuclide generator
Unit Dose	40 mcg per kit	1850 MBq (50 mCi)
Strength(s)		
Dosage Level(s)	[⁶⁸ Ga]Ga-DOTA-TATE will be administered at a dose of 2 MBq/kg (0.054 mCi/kg) of body weight up to a maximum total dose of 200 MBq (5.4 mCi)	NA
Route of Administration	Intravenous use	NA
Use	(After radiolabeling with Ga-68)	
IMP	experimental	experimental
Sourcing	Yes ([⁶⁸ Ga]Ga-DOTA-TATE, after radiolabeling with Ga-68)	Yes, Radionuclide generator
Packaging and Labeling	Provided centrally by the sponsor (global)	Provided centrally by the sponsor (global)
	Study treatment will be provided as a kit. Each kit will be labeled as required per country requirement.	The ⁶⁸ Ge/ ⁶⁸ Ga Generator is presented as a stainless-steel case

6.1.1 Additional study treatments

No other treatment beyond investigational drug and control drug are included in this trial.

6.1.2 Treatment arms/group

Not applicable for this study because there is only one treatment arm.

6.1.3 Guidelines for continuation of treatment

Not applicable for this study.

6.1.4 Treatment duration

[⁶⁸Ga]Ga-DOTA-TATE will be administered intravenously at a dose of 2 MBq/kg (0.054 mCi/kg) of body weight up to a maximum total dose of 200 MBq (5.4 mCi) at the imaging day.

6.1.4.1 Treatment beyond disease progression

Not applicable.

6.1.5 Medical devices

Not applicable.

6.2 Preparation, handling, storage, and accountability

Each study site will be supplied with study treatment in packaging as described under [Table 6-1](#) Investigational and control drugs section.

The DOTA-TATE as a sterile two-vials kit and the $^{68}\text{Ge}/^{68}\text{Ga}$ Generator will be supplied by Sponsors to hospital's radiopharmacies. The elution of the $^{68}\text{Ge}/^{68}\text{Ga}$ Generator and the reconstitution of the kit with the eluate for radiolabeling will be performed at clinical trial sites.

[^{68}Ga]Ga-DOTA-TATE must be prepared and administered by qualified/authorized personnel only in accordance with pharmaceutical quality requirements and radiation safety regulations.

After reconstitution, [^{68}Ga]Ga-DOTA-TATE solution will be administered by intravenous injection.

The instructions and explanations for ordering, delivery, elution of the $^{68}\text{Ge}/^{68}\text{Ga}$ Generator, radiolabeling procedure and dispensing of [^{68}Ga]Ga-DOTA-TATE, as well as cautionary notes, analytical controls and stability information for the radiolabeled product will be provided to each site (please refer to the Pharmacy Manual).

6.2.1 Handling of study treatment

Study treatment must be received by a designated person at the study site, handled and stored safely and properly and kept in a secured location to which only the Investigator and designated site personnel have access. Upon receipt, all study treatment must be stored according to the instructions specified in the Investigator's Brochure.

Clinical supplies are to be dispensed only in accordance with the protocol.

Medication labels will be in the local language and comply with the legal requirements. They will include storage conditions for the study treatment but no information about the participant.

The Investigator or designated site staff must maintain an accurate record of the shipment and dispensing of study treatment in a drug accountability log. Monitoring of drug accountability will be performed by field monitors during site or remote monitoring visits, and at the completion of the trial. It must be possible to reconcile delivery records with those of used and unused medication. Any discrepancies must be accounted for and explained. Appropriate forms of deliveries and returns must be signed and dated by the responsible person at the clinical site and maintained as records. The return or disposal of all study medication will be documented appropriately.

For more details about technical complaints, the handling of [^{68}Ga]Ga-DOTA-TATE refer to the Pharmacy Manual.

6.2.2 Handling of other treatment

Not applicable.

6.2.3 Instruction for prescribing and taking study treatment

For further details on the [⁶⁸Ga]Ga-DOTA-TATE administration refer to Section 6.1 and to Pharmacy Manual.

6.3 Measures to minimize bias: randomization and blinding

6.3.1 Treatment assignment, randomization

Not applicable.

6.3.2 Treatment blinding

The following blinding is applicable in this study:

- [⁶⁸Ga]Ga-DOTA-TATE PET/CT imaging will be submitted to a CRO for independent centralized read by 3 independent readers blinded to CIM and patient data collected in clinical database.
- CIM will be submitted to a CRO for independent centralized read by 1 independent reader, blinded to [⁶⁸Ga]Ga-DOTA-TATE PET/CT imaging and patient data collected in clinical database.

6.3.3 Emergency breaking of assigned treatment code

Not applicable.

6.4 Study treatment compliance

All participants will have the study treatment administered during site visits on imaging day. All study treatments must be recorded in the Drug Accountability Log and in the corresponding eCRF pages.

6.5 Dose modification

Dose modifications are not applicable in this study for the investigational imaging agent which is administered intravenously as a single dose.

6.5.1 Definitions of dose limiting toxicities (DLTs)

Not applicable.

6.5.2 Dose modifications

Not applicable.

6.5.3 Follow-up for toxicities

Not applicable.

6.5.3.1 Follow up on potential drug-induced liver injury (DILI) cases

Not applicable.

6.6 Continued access to study treatment after the end of the study

Not applicable.

6.6.1 Post trial access

Not applicable.

6.7 Treatment of overdose

In the event of administration of a radiation overdose with investigational agent, the radiation absorbed dose to the participant should be reduced where possible by increasing the elimination of the radionuclide from the body by frequent micturition or by forced diuresis and frequent bladder voiding. It might be helpful to estimate the effective radiation dose that was applied.

In the event of an overdose, the Investigator/treating physician should:

- Contact the medical monitor immediately.
- Document the quantity of the excess dose as well as the duration of the overdose.
- Follow standard clinical practice for overdose of diagnostic radiopharmaceuticals.

6.7.1 Reporting of study treatment errors including misuse/abuse

Medication errors are unintentional errors in the prescribing, dispensing, administration or monitoring of a medicine while under the control of a healthcare professional, participant or consumer (EMA definition).

Misuse refers to situations where the medicinal product is intentionally and inappropriately used not in accordance with the protocol.

Abuse corresponds to the persistent or sporadic, intentional excessive use of a medicinal product, which is accompanied by harmful physical or psychological effects.

Study treatment errors and uses outside of what is foreseen in the protocol will be recorded on the appropriate CRF irrespective of whether or not associated with an AE/SAE. Study treatment errors and uses outside of what is foreseen in the protocol, misuse or abuse will be collected and reported in the safety database irrespective of it being associated with an AE/SAE within 24 hours of Investigator's awareness. For more information on AE and SAE definition and reporting requirements, please see the respective sections.

6.8 Concomitant and other therapy

- Use of diuretics (e.g. furosemide) to help the subject voiding before PET/CT acquisition is allowed in case of need, upon the discretion of the Investigator, and should be captured in the eCRF like other concomitant medications.

6.8.1 Concomitant therapy

All medications, procedures, and significant non-drug therapies (including physical therapy and blood transfusions) administered after the participant was enrolled into the study must be recorded on the appropriate eCRF.

Each concomitant drug must be individually assessed against all exclusion criteria and prohibited medication. If in doubt, the Investigator should contact the Novartis, Eckert & Ziegler Radiopharma GmbH medical monitor before enrolling a participant or allowing a new medication to be started. If the participant is already enrolled, contact Novartis, Eckert & Ziegler Radiopharma GmbH to determine if the participant should continue participation in the study.

Use of diuretics (e.g. furosemide) to help participants voiding before PET/CT acquisition is allowed in case of need, upon the discretion of the Investigator.

6.8.1.1 Permitted concomitant therapy requiring caution and/or action

Some evidence exists that corticosteroids can induce down-regulation of SSTR2. Repeated administration of high-doses of corticosteroids prior to [⁶⁸Ga]Ga-DOTA-TATE administration may cause insufficient SSTR2 expression for adequate visualization of SSTR-positive tumors.

6.8.1.2 Use of bone modifying agents

Not applicable.

6.8.2 Prohibited medication

HV participants

Except for protocol allowed concomitant medication and/or any medication which may be required to treat adverse events [and permitted oral or injectable contraceptives for female participants], no medication other than study treatment will be allowed from the date participant signs the informed consent until all of the study completion evaluations have been performed.

NENs patients

Somatostatin analogues competitively bind to the same SSTR as [⁶⁸Ga]Ga-DOTA-TATE. Refer to Section 5.2 for washout period prior to [⁶⁸Ga]Ga-DOTA-TATE imagings.

7 Discontinuation of study treatment and participant discontinuation/withdrawal

7.1 Discontinuation of study treatment

Since [⁶⁸Ga]Ga-DOTA-TATE is administered as a single intravenous injection, discontinuation of [⁶⁸Ga]Ga-DOTA-TATE is not applicable.

7.2 Participant discontinuation from the study

Discontinuation from study is when the participant permanently stops receiving the study treatment, and further protocol-required assessments or follow-up, for any reason.

If the participant agrees, a final evaluation at the time of the participant's study discontinuation should be made as detailed in [Section 1.3](#) Schedule of Activities.

7.3 Withdrawal of informed consent and exercise of participants' data privacy rights

Withdrawal of consent/opposition to use of data and/or biological samples occurs when a participant:

- Explicitly requests to stop use of their data
and
- No longer wishes to receive study treatment
and
- Does not want any further visits or assessments (including further study-related contacts)

This request should be made as per local regulations (e.g. in writing) and recorded in the source documentation.

Withdrawal of consent impacts ability to further contact the participant, collect follow-up data (e.g. to respond to data queries) and potentially other country-specific restrictions. It is therefore very important to ensure accurate recording of withdrawal vs. discontinuation based on the protocol definitions of these terms.

In this situation, the Investigator should make a reasonable effort (e.g. telephone, e-mail, letter) to understand the primary reason for the participant's decision to withdraw their consent/exercise data privacy rights and record this information. The Investigator shall clearly document if the participant has withdrawn his/her consent for the use of data in addition to a study discontinuation.

Study treatment must be discontinued and no further assessments conducted.

Further attempts to contact the participant are not allowed unless safety findings require communicating or follow-up.

If the participant agrees, a final evaluation at the time of the participant's withdrawal of consent/exercise data privacy rights should be made as detailed in [Section 1.3](#) Schedule of Activities.

Further details on withdrawal of consent or the exercise of participants' data privacy rights are included in the corresponding informed consent form.

7.4 Lost to follow-up

For participants whose status is unclear because they fail to appear for study visits or fail to respond to any site attempts to contact them without stating an intention to discontinue from study treatment or discontinue, the Investigator must document "due diligence" steps taken to contact the participant, e.g. dates of telephone calls, registered letters in the source documents. A participant should not be considered as lost to follow-up until due diligence has been completed or until the end of the study.

7.5 Early study termination by the Sponsor

The study can be terminated by Novartis, Eckert & Ziegler Radiopharma GmbH at any time.

Reasons for early termination (but not limited to)

- Unexpected, significant, or unacceptable safety risk to participants enrolled in the study
- Decision based on recommendations from applicable board(s) after review of safety and efficacy data
- Discontinuation of study treatment development in this indication

In taking the decision to terminate, Novartis, Eckert & Ziegler Radiopharma GmbH will always consider participant welfare and safety. Should early termination be necessary, participants must be seen as soon as possible and treated as a participant who discontinued from study treatment (e.g. safety follow up period must be completed if applicable with required visits to be performed). The Investigator may be informed of additional procedures to be followed in order to ensure that adequate consideration is given to the protection of the participant's interests. The Investigator or Novartis, Eckert & Ziegler Radiopharma GmbH depending on local regulation will be responsible for informing IRBs/IECs of the early termination of the trial.

8 Study Assessments and Procedures

- Study procedures and their timing are summarized in [Section 1.3](#) Schedule of Activities. Protocol waivers or exemptions are not allowed.
- Immediate safety concerns should be discussed with Novartis, Eckert & Ziegler Radiopharma GmbH upon occurrence or awareness to determine if the participant should continue or discontinue study treatment.
- Adherence to the study design requirements, including those specified in [Section 1.3](#) Schedule of Activities, is essential and required for study conduct.
- Repeat or unscheduled samples may be taken for safety reasons or for technical issues with the samples.

8.1 Screening

Screening

Written informed consent must be obtained prior to any screening procedures. Please refer to [Section 10.1.2](#) for the Informed Consent procedures.

All screening assessments should occur within 35 days prior to imaging day. CIM assessment performed as a part of clinical practice within 2 months prior to imaging day even before informed consent, can be used as standard reference as long as imaging quality meets study defined criteria. Refer to Imaging Manual for details.

It is permissible to re-screen (only once) a participant if he or she fails the initial screening (screen failure); however, each case must be discussed and agreed with the Sponsor on a case-by-case basis. Re-screening should not be performed for avoiding the eligibility criteria, putting the participant at safety risk. Re-screened participants will need to be re-consented and a new Participant Number will be assigned. Re-screening tests should be repeated as per

inclusion/exclusion requirements and re-screening should be documented in the source documents.

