2.2 Background

NENs are malignant tumors that develop in the lungs, gastrointestinal tract, and other organs and show various clinical symptoms. The most common primary site varies by race, with the lung being the most common in white patients, and the rectum being the most common in Asian patients (Yao et al 2008). Gastroenteropancreatic NENs are common in the Japanese population and the age-adjusted incidence rate of gastroenteropancreatic NENs was approximately 3.5 cases/year per 100,000 people in Japan (Masui et al 2020). Neuroendocrine markers (synaptophysin, chromogranin A, etc.), various diagnostic imaging technologies (ultrasonography, CT, MRI, FDG-PET/CT, somatostatin receptor (SSTR) scintigraphy), and histopathologies are used in diagnosis of NENs (Clinical Practice Guidelines for Gastroenteropancreatic Neuroendocrine Neoplasms 2019). The treatment of NENs is mainly radical surgery and drug therapy, and the first-line curative treatment is surgical resection when tumors are localized. Hence, accurate localization diagnosis and disease staging are important to determine the indication for surgery.

A distinct feature shared by NENs is the over-expression of SSTRs, particularly SSTR type 2 (SSTR2), on the membrane's plasma, which makes SSTRs suitable molecular targets for specific diagnostic and therapeutic ligands (Reubi 2003, Volante et al 2007). This has led to the approval of $[^{177}\text{Lu}]\text{Lu}\text{-DOTA-TATE}$, a radioligand therapy targeting SSTR, in Japan in 2021 for the indication of "somatostatin receptor-positive neuroendocrine tumors". In order to select appropriate patients for this new drug therapy, it is important to confirm the SSTR expression.

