3.1 Primary estimands

The primary clinical question of interest is: What is the probability that [⁶⁸Ga]Ga-DOTA-TATE PET/CT imaging truly detects tumor lesion(s) in subject-level for NENs using CIM (including [¹¹¹In]In-Pentetreotide SPECT/CT and High Resolution CT with contrast (or MRI if CT with contrast is medically contraindicated) as standard of truth).

The justification for the primary estimand is that it will capture the diagnostic performance of [⁶⁸Ga]Ga-DOTA-TATE PET/CT imaging in detecting tumor lesion(s) in NENs subjects. For this reason, participants with confirmed or suspected NENs will be investigated with CIM obtained on or before screening phase (HVs will be categorized as CIM negative without performing CIM) and confirmed or suspected NENs and HVs will be investigated with [⁶⁸Ga]Ga-DOTA-TATE PET/CT imaging on treatment phase, and the results of [⁶⁸Ga]Ga-DOTA-TATE PET/CT imaging will be compared against the results of CIM as standard of truth.

The primary estimands are described by the following attributes:

Primary estimand 1:

1. Population: Patients who show at least one lesion based on CIM by central read, received [⁶⁸Ga]Ga-DOTA-TATE, completed a PET/CT scan and had a central read of the [⁶⁸Ga]Ga-DOTA-TATE PET/CT imaging.
2. Variable: The result of [⁶⁸Ga]Ga-DOTA-TATE PET/CT imaging (positive (i.e., showing at least one lesion) or negative (i.e., not showing any lesion)). In the population above, a participant with positive [⁶⁸Ga]Ga-DOTA-TATE PET/CT imaging corresponds to True positive (TP) and a participant with negative on [⁶⁸Ga]Ga-DOTA-TATE PET/CT imaging corresponds to False negative (FN).
3. Treatment of interest: [⁶⁸Ga]Ga-DOTA-TATE injected as a single intravenous dose of 2 MBq/kg (0.054 mCi/kg) of body weight up to a maximum total dose of 200 MBq (5.4 mCi).
4. Intercurrent events: None
5. Summary measure: Estimate of proportion of participants who test positive on [⁶⁸Ga]Ga-DOTA-TATE PET/CT imaging (TP) among those who are CIM positive (TP+FN)

according to [⁶⁸Ga]Ga-DOTA-TATE PET/CT imaging) (subject-level sensitivity), along with 95% confidence interval.

Primary estimand 2:

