5.2 Exclusion criteria

Participants meeting any of the following criteria are not eligible for inclusion in this study.

1. Any additional medical condition, serious intercurrent illness, concomitant cancer or other extenuating circumstance that, in the opinion of the Investigator, would indicate a significant risk to safety or impair study participation.
2. Inability to complete the needed investigational and conventional imaging due to any reason (severe claustrophobia, inability to lie still for the entire imaging time, etc.)
3. Known allergy, hypersensitivity, or intolerance to [⁶⁸Ga]Ga-DOTA-TATE and [¹¹¹In]In-Pentetreotide
4. Therapeutic use of any somatostatin analogue except for the following washout period
 - Short-acting analogs of somatostatin can be used up to 24 hours before injection with [⁶⁸Ga]Ga-DOTA-TATE
 - Long-acting analogs of somatostatin can be used up to 28 days before injection of [⁶⁸Ga]Ga-DOTA-TATE
5. Prior administration of a radiopharmaceutical unless 10 or more half-lives have elapsed before injection of [⁶⁸Ga]Ga-DOTA-TATE
6. Use of other investigational drugs within 30 days before screening
7. Participants who are pregnant.
8. Participants who are lactating.

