9.3.1 Definition of primary endpoint(s)

The co-primary endpoints of the study are subject-level sensitivity and specificity.

Subject-level sensitivity

Subject-level sensitivity is defined as the proportion of [⁶⁸Ga]Ga-DOTA-TATE PET/CT imaging positive participants (i.e. TP participants) among CIM positive participants (i.e. TP or FN participants).

Subject-level specificity

Subject-level specificity is defined as the proportion of [⁶⁸Ga]Ga-DOTA-TATE PET/CT imaging negative participants (i.e. TN participants) among CIM negative participants (i.e. TN or FP participants).

Table 9-1 Sensitivity and Specificity

		Conventional Imaging (CIM)	
		Positive	Negative
[⁶⁸ Ga]Ga-DOTA-TATE PET/CT imaging	Positive	True Positive (TP)	False Positive (FP)
	Negative	False Negative (FN)	True Negative (TN)

Sensitivity: TP / (TP + FN), Specificity: TN / (TN + FP)

Where TP, FP, TN, FN participants are defined as follows:

- TP participants are those who show at least one lesion based on both [⁶⁸Ga]Ga-DOTA-TATE PET/CT imaging and CIM by central read.

- FP participants are those who show at least one lesion based on [⁶⁸Ga]Ga-DOTA-TATE PET/CT imaging but do not show any lesion based on CIM by central read.
- TN participants are those who do not show any lesion based on both [⁶⁸Ga]Ga-DOTA-TATE PET/CT imaging and CIM by central read.
- FN participants are those who do not show any lesion based on [⁶⁸Ga]Ga-DOTA-TATE PET/CT imaging but show at least one lesion based on CIM by central read.

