2.5.1 Primary endpoint(s)

The co-primary endpoints of the study are subject-level sensitivity and specificity.

Subject-level sensitivity

Subject-level sensitivity is defined as the proportion of $[^{68}\text{Ga}]\text{Ga}\text{-DOTA-TATE}$ PET/CT imaging positive participants (i.e. TP participants) among CIM positive participants (i.e. TP or FN participants).

Subject-level specificity

Subject-level specificity is defined as the proportion of $[^{68}\text{Ga}]\text{Ga}\text{-DOTA-TATE}$ PET/CT imaging negative participants (i.e. TN participants) among CIM negative participants (i.e. TN or FP participants).

Table 2-2 Sensitivity and Specificity

		Conventional Imaging (CIM)	
		Positive	Negative
$[^{68}\text{Ga}]\text{Ga}\text{-DOTA-TATE}$ PET/CT imaging	Positive	True Positive (TP)	False Positive (FP)
	Negative	False Negative (FN)	True Negative (TN)
Sensitivity: TP / (TP + FN), Specificity: TN / (TN + FP)			

Where TP, FP, TN, FN participants are defined as follows:

- TP participants are those who show at least one lesion based on both $[^{68}\text{Ga}]\text{Ga}\text{-DOTA-TATE}$ PET/CT imaging and CIM by central read.
- FP participants are those who show at least one lesion based on $[^{68}\text{Ga}]\text{Ga}\text{-DOTA-TATE}$ PET/CT imaging but do not show any lesion based on CIM by central read.
- TN participants are those who do not show any lesion based on both $[^{68}\text{Ga}]\text{Ga}\text{-DOTA-TATE}$ PET/CT imaging and CIM by central read.

- FN participants are those who do not show any lesion based on [⁶⁸Ga]Ga-DOTA-TATE PET/CT imaging but show at least one lesion based on CIM by central read.

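### Neither document has a rule for anticancer treatment between the reference CIM and the PET/CT, so a patient fully cleared of disease in that gap would count as a PET false negative

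*Protocol*

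**What the plan says.** **The reference scan.** Screening procedures fall within 35 days before imaging day. As an explicit exception, Protocol 8.1, Table 1-2 footnote 4 and the Table 8-2 footnote accept a clinical-practice CIM from up to 2 months before PET. Beyond that time limit, the one stated condition is quality: in 8.1, a CIM performed "within 2 months prior to imaging day even before informed consent, can be used as standard reference as long as imaging quality" meets the study's criteria. Section 8.1 then adds "Refer to Imaging Manual for details". That manual was not among the documents supplied.

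**Eligibility.** Inclusion criterion 4 accepts NEN confirmed by histopathology, imaging and other examination, without requiring disease to be present on the day of PET. The treatment-specific exclusions in Protocol 5.2 concern somatostatin analogues, prior radiopharmaceuticals and "Use of other investigational drugs within 30 days before screening". None names surgery, ablation, external radiotherapy or marketed systemic treatment. For patients, registration (8.1.1) checks the centrally read CIM result.

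**Scoring.** SAP 2.5.1 defines a subject-level false negative as a participant with no lesion on the DOTA-TATE "PET/CT imaging but show at least one lesion based on CIM by central read". Protocol 9.3.1 says the same, and the region-level definition is parallel.

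**Estimand and analyses.** Both primary estimands in Protocol 3.1 state "Intercurrent events: None". The Efficacy Analysis Set (EFF) drops participants who were not dosed or whose reads are missing or not evaluable. Sensitivity analyses are not applicable. The supplementary analyses in SAP 2.5.6 cover individual readers, participants outside the EFF, suboptimal images and subgroups, and run only if the primary endpoints are met.

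**The concern.** The co-primary question is whether PET detects tumour that is there. That requires the reference and the index test to describe the same disease state. Protocol 2.2 says that "the first-line curative treatment is surgical resection when tumors are localized", so a positive CIM can itself lead to removal of the disease it showed.

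Take a patient with localized NEN who has a positive CIM, then a complete resection with confirming histology, then PET. As far as the two documents go, this patient is eligible, is registered as CIM positive, and enters the sensitivity denominator. A correct negative PET is recorded as a miss.

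The same mechanism lowers NPV, since the extra false negative enters its denominator, and region-level sensitivity and NPV wherever a whole region was cleared. It also distorts the lesion counts compared between PET and CIM. Subject-level specificity is untouched by such a patient, who is not in the CIM-negative group.

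Because the supplementary analyses run only after success, no planned analysis would look into a failure that arose this way.

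**Working it through.** **Inputs** (Protocol 9.3.2 and 9.9.1; SAP 2.5.2 and 3): N = 47 CIM-positive patients, expected sensitivity 0.90, threshold 0.70, one-sided alpha 2.5%. Success means the exact 95% lower bound exceeds 0.70.

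**1. Success rule as a count.** The Clopper-Pearson lower bound is 0.717 at 40/47 and 0.692 at 39/47. Success therefore needs at least 40 true positives, so at most 47 − 40 = 7 false negatives. At 90% sensitivity, 47 × 0.10 = 4.7 are expected.

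**2. The plan's own figure.** P(X ≥ 40) with X ~ Bin(47, 0.90) is 0.907, matching the 90.7% in Protocol Table 9-3 and SAP Table 3-1. The other five sensitivity rows and all six specificity rows also reproduce.

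**3. Effect of cleared patients.** Let k of the 47 have no PET-visible disease left at PET because of treatment after the CIM. They are certain false negatives, so the 40 true positives must come from the other 47 − k:

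- Power = P(Bin(47 − k, 0.90) ≥ 40)
- Expected observed sensitivity = 0.90 × (47 − k)/47
- Chance of false success if true sensitivity is 0.70 = P(Bin(47 − k, 0.70) ≥ 40)

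| k (assumed) | Other false negatives still tolerated | Expected observed sensitivity | Power | False success at 0.70 |
|---|---|---|---|---|
| 0 | 7 of 47 | 90.0% | 90.7% | 1.38% |
| 1 | 6 of 46 | 88.1% | 82.8% | 0.63% |
| 2 | 5 of 45 | 86.2% | 70.8% | 0.26% |
| 3 | 4 of 44 | 84.3% | 54.7% | 0.09% |

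**4. Smaller denominator.** Up to 5 CIM-negative patients are allowed, so N for sensitivity can be as low as 42, where success needs 36 true positives. Power is then 87.9%, 77.7%, 62.9% and 44.4% for k = 0 to 3.

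**5. If such patients are left out instead.** With N = 47 − k, power is 91.6% (k=1), 92.4% (k=2) and 85.4% (k=3), the plan's own values for 46, 45 and 44. If they are left out and enrolment continues to 47 CIM-positive patients, power stays at 90.7%.

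**The case against.** **A treated tumour is not automatically a false negative.** A reader might infer that any lesion resected or treated in the gap is scored against PET. The definitions do not support that. Subject-level false negative requires PET to show no lesion anywhere; a treated lesion still visible, or any other visible disease, keeps the patient a true positive. At region level the whole region must be cleared. This stands, and it confines the problem to complete clearance.

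**Such patients may be rare.** A reader might also take the resected patient as typical. Protocol 4.2 and 8.3.3 describe NEN patients as often metastatic at diagnosis. The questionnaire records the intended treatment plan before and after PET, and biopsy or surgery is foreseen within 30 days after imaging. All this suggests PET ahead of treatment. No passage gives a rate of treatment between the scans. This stands: the frequency is unknown.

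**Other safeguards may exist.** The Imaging Manual and registration manual were not supplied and may add conditions. Exclusion criterion 1 lets the investigator exclude for other circumstances that impair participation, but this is discretionary. SAP 2.1 uses the latest scan of a modality, which helps only if that modality was repeated after treatment. The same section prefers MRI over CT without reference to date. These points soften the gap without closing it; a rule that fixes the co-primary reference belongs in the protocol.

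**The 2-month window is not the cause.** A CIM from the ordinary 35-day window raises the same issue. This stands, so the fix must cover every CIM.

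**The error works against the product.** This stands too: the chance of false success falls as k rises, so a positive result would not be undermined.

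**Conclusion.** The point holds within limits. The two documents fix the reference result at the CIM and have no rule for anticancer treatment between it and the PET/CT. A patient whose PET-visible disease was completely cleared in that gap would be counted as a false negative in the co-primary sensitivity despite a correct PET.

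The size depends wholly on k, which the documents do not give. k = 0 is compatible with everything in them, and 1 to 3 is an assumed range. The calculation also assumes 90% sensitivity in all other patients. Within that range a single patient matters: with only 7 misses allowed and 4.7 expected, k = 1 costs about 8 percentage points of power (90.7 − 82.8 = 7.9).

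The documents do not support reading this as a threat to the validity of a positive finding. The consequences are lower power, downward bias in sensitivity and NPV, and distorted lesion counts. Whether the Imaging Manual already closes the gap cannot be judged here.

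**What to change.** 1. **Protocol 8.1, Table 1-2 footnote 4 and the Table 8-2 footnote.** State that any CIM, whether from clinical practice or from screening, serves as standard of truth only if no tumour-directed surgery, locoregional procedure or radiotherapy, and no newly started systemic antineoplastic treatment, took place between it and the PET/CT. This is a condition on the reference scan and leaves patient care unchanged.

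2. **SAP 2.5.6.** Add a supplementary analysis of both co-primary endpoints, run whatever the primary result, that excludes participants with such treatment in the interval. List those participants with their CIM, treatment and PET dates.

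**Cost.** A few added lines of text and one analysis. Prior antineoplastic medication, radiotherapy and surgery, and concomitant procedures, are already collected and listed (Protocol 8.2 and Table 1-2; SAP 2.4.2).

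**Downside.** A few patients with an outdated CIM would not qualify on that scan. The exclusion analysis also drops some treated patients who were correctly scored true positive, so it does not isolate the error; the listing lets a reader see which cases matter.
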